1.5 Risks and Benefits

• The benefits of methylene blue:

Methylene blue causes vasoconstriction by inhibiting nitric oxide synthase and preventing subsequent activation of guanylyl cyclase in smooth muscle cells. This reaction increases systemic blood pressure and decreases vasopressor requirements for patients with vasoplegic syndrome. In LT surgery patients, hemodynamic stability without the requirements of vasopressors may allow immediate extubation at the end of the surgery and bypass the intensive care unit in the postoperative period, allowing faster recovery and improving outcomes. Advocates for early extubation have argued that it may be beneficial for the new organ graft to limit the exposure to mechanical ventilation. Kaisers et al reported the deleterious effects of positive end expiratory pressure (PEEP) on liver graft hemodynamics.

• The risks of methylene blue:

Common side effects include hypertension, discoloration of skin, hyperhidrosis, nausea, dizziness, headache, pain in limb, and abnormal urine color, hypersensitivity, hemolytic anemia

Medications which may accumulate with methylene blue due to inhibition of cytochrome P450 isozymes: Alfentanil, cyclosporine, digoxin, fentanyl, phenytoin, sirolimus, tacrolimus, warfarin.

Methylene blue is contraindicated in patients with glucose-6-phosphate dehydrogenase (G6PD) deficiency as it can result in a hemolytic response in patients with G6PD deficiency. The intravascular hemolysis typically occurs two to five days after drug administration and is typically self-limited.

Methylene blue may cause serotonin syndrome when used in combination with serotonergic drugs such as Selective serotonin reuptake inhibitors (SSRIs), serotonin and norepinephrine reuptake inhibitors (SNRIs), and monoamine oxidase inhibitors (MAOIs).

- The benefits of hydroxocobalamin: IV hydroxocobalamin is currently approved for cyanide poison treatment. Its ability to bind and inhibit the 3 main gasotransmitters (nitric oxide, carbon monoxide, and hydrogen sulfide) contributing to vasoplegic syndrome has made it a new treatment for intraoperative vasoplegic syndrome. Unlike methylene blue, it does not have the same implications in serotonin syndrome. Similar to the benefits of methylene blue on treating vasoplegic syndrome, hydroxocobalamin may play a major role to allow hemodynamic stability and early extubation in this particular LT population.
- The risks of hydroxocobalamin: Common side effects include increased blood pressure, erythema, rash, nausea, decreased lymphocyte count, headache, and abnormal red urine color.

2 Study Objectives

Primary Objective

To assess the efficacy of hydroxocobalamin as compared to methylene blue on improving hemodynamic stability as measured by SVR, systemic blood pressure, and amount of vasopressors administered.

Secondary Objective

The secondary end point will examine the patient outcomes in the postoperative period as measured by early tracheal extubation after surgery, length of hospital and intensive care unit stay, perioperative complications (stroke, myocardial infarction, and acute renal failure), graft function, and survival rate.

3 Study Design

3.1 General Description

This randomized, prospective, open label, pilot study will involve 20 LT patients with intraoperative vasoplegic syndrome. If vasoplegic syndrome is identified via SVR lower than 500 dynes-sec/cm⁻⁵, the patients will be randomized to receiving either IV methylene blue or hydroxocobalamin (10 patients in each group). The administration of assigned medication will only take place once during surgery if patient is exhibiting vasoplegia after the reperfusion of the new organ as demonstrated by SVR lower than 500 dynes-sec/cm⁻⁵ sustained for a period of more than 5 minutes despite the administration of vasopressors. The primary end point will examine the efficacy of the two medications on treating intraoperative vasoplegic syndrome. The SVR, blood pressure, and amount of administrations will be recorded.

[figure not shown]
If the patients still present with vasoplegic syndrome 30 minutes after receiving IV methylene blue or hydroxocobalamin during LT surgery, the vasoplegia treatment which the patients have not received in the operating room would be utilized as life-saving measures per standard of care practice. The patients will be excluded from the comparison study, but the data of frequency of failure to effectively treat vasoplegia via certain medication may be utilized in understanding the rate of failure to provide effective treatment.

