1.3 Clinical Data to Date

A comprehensive search of the terms "hydroxocobalamin," "vitamin B12," "Cyanokit," "vasoplegia," "vasoplegic syndrome," and "liver transplantation" within MEDLINE and Embase was performed. Only 3 case reports with a total of 4 individual patients receiving B12 for the treatment of VS during LT surgeries were yielded from the MEDLINE search from 1946 to 2018 and Embase from 1988 to 2018. Although all 4 patients were reported to have favorable responses after B12 administration consistent with improved hemodynamics and reduced vasopressor requirements, no statistically significant conclusion could be drawn from the limited number of case reports.

A retrospective chart review was conducted for LT surgeries performed at our institution between January 2016 and June 2018. For patients with post-reperfusion VS treated with vasopressors, MB, and B12, hemodynamics variables and vasopressor requirements were reviewed. Fourteen of 401 LT patients during the study period presented with intraoperative VS and received vasopressors and MB as the first-line VS treatment due to the institutional protocol. Nine out of 14 patients receiving MB had an ineffective response defined as failure to improve hemodynamics or to reduce pressor requirements and were subsequently administered B12. Favorable changes in hemodynamic parameters with minimal averaged change of vasopressor requirements were observed after B12 administration. No major side-effect, medication associated complication, and post-operative mortality within 6 months of LT was observed. The institutional protocol required the usage of MB before B12 for VS treatment, causing the retrospective chart review to have clear comparison on the effectiveness of the 2 medications.

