3.4 Primary Study Endpoints

The primary endpoint of the study will be the improvement in hemodynamic values as measured by SVR, systemic blood pressure, and amount of vasopressors administered. The monitoring and documentation of hemodynamic values is part of SOC practice during LT surgery.

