4.4 Early Withdrawal of Subjects

4.4.1 When and How to Withdraw Subjects

Patients are free to withdraw at any time and for whatever reason. No data will be collected for withdrawn subjects. Withdrawn subjects may be replaced during the accrual period. Prespecified reasons for discontinuing include, but are not limited to, the following:

- Patient Request: Patient decided that he/she did not want to continue (for any reason)
- Adverse Event: Patient experienced a related or unrelated event that would interfere with the study objectives/evaluation
- Treatment Failure: If in the Principal Investigator and/or Investigators' judgment, the patient's condition required another form of treatment
- Inclusion/Exclusion Discrepancy/Violation: Patient should not have been enrolled
- Noncompliance: Patient is not complying with the protocol requirements (i.e. visit schedule, dosing, regimen, etc.); a patient is to be withdrawn if he/she misses two consecutive visits
- Other: Any other reason

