7.1 Sample Size Determination

Per the biostatistician from the Mayo Division of Biomedical Statistics and Informatics, the existing information on the changes of SVR, blood pressure, and amount of administered vasopressors altered by either medication are not sufficient for sample size calculation. The primary aim of this pilot study will be to determine feasibility and to collect descriptive data that can be used in future to obtain statistical power.

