7.3 Subject Population(s) for Analysis

Each participant who received the study drug will be included in the primary analysis regardless of study withdrawal for any reason. In the event of any study withdrawals, in secondary analysis we will examine the sensitivity of our results to the exclusion of patients who withdrew.

8 Safety and Adverse Events

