9.1 Confidentiality

Information about study subjects will be kept confidential and managed according to the requirements of the Health Insurance Portability and Accountability Act of 1996 (HIPAA). Those regulations require a signed subject authorization informing the subject of the following:

- What protected health information (PHI) will be collected from subjects in this study
- Who will have access to that information and why
- Who will use or disclose that information
- The rights of a research subject to revoke their authorization for use of their PHI.

In the event that a subject revokes authorization to collect or use PHI, the investigator, by regulation, retains the ability to use all information collected prior to the revocation of subject authorization. For subjects that have revoked authorization to collect or use PHI, attempts should be made to obtain permission to collect at least vital status (long term survival status that the subject is alive) at the end of their scheduled study period.

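### Section 3.1 removes treated patients who are still vasoplegic at 30 minutes from the drug comparison; this selects on the primary outcome and contradicts section 7.3

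*Combined protocol and SAP*

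**What the plan says.** - **Section 3.1 (General Description)** identifies vasoplegic syndrome by SVR below 500 and plans 10 patients per arm. A patient who is still vasoplegic 30 minutes after the assigned drug receives the other one. Of these patients it says: "The patients will be excluded from the comparison study". How often each drug failed is something the section only permits to be used.
- **Section 3.4 (Primary Study Endpoints)** measures improvement by SVR, systemic blood pressure and vasopressor amount. It names no time point.
- **Section 7.3 (Subject Population(s) for Analysis)** sets a different rule: "Each participant who received the study drug will be included in the primary analysis regardless of study withdrawal for any reason". Leaving out patients who withdrew is a secondary sensitivity analysis.
- **Section 4.4.1 (When and How to Withdraw Subjects)** lists treatment failure, meaning a need for another treatment in the investigators' judgment, among the reasons for discontinuing. It also says: "No data will be collected for withdrawn subjects. Withdrawn subjects may be replaced during the accrual period".
- **Section 7.1 (Sample Size Determination)** gives the pilot's aims as feasibility and to "collect descriptive data that can be used in future to obtain statistical power".

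**The concern.** A treated patient who has not responded at 30 minutes is out of the comparison under 3.1 and in the primary analysis under 7.3. Section 4.4.1 makes this harder to resolve. It does not say whether a 3.1 exclusion is a withdrawal, or whether its no-data rule stops further collection only or also bars use of what is already recorded. On the strictest reading, 7.3 could not be carried out for treatment failures, and replacement could refill the arms with responders.

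The 3.1 rule would be a problem even without the conflict. Exclusion depends on a value of the primary endpoint measured after randomization. The patients who show that a drug did not work leave the efficacy comparison, and the two arms keep differently selected patients. The later trial would then be planned on a distorted difference and, for 30-minute SVR, on an SD that is too small. Postoperative outcomes restricted to responders would be selected in the same way.

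**Working it through.** The plan derives no sample size, power or effect figure, so there is nothing of its own to reproduce. The contradiction needs no arithmetic. The steps below show how large the effect of the 3.1 rule could be.

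**Inputs from the document**
- 10 patients per arm (3.1).
- SVR threshold of 500 (3.1). I assume the 30-minute check uses the same threshold; 3.1 does not restate it.
- Methylene blue failure rate (1.3): "Nine out of 14 patients receiving MB had an ineffective response defined as failure to improve hemodynamics or to reduce pressor requirements". This is a retrospective series, and its definition is not the 30-minute rule.

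**Assumptions**
- The document gives no SVR SD and no first-line hydroxocobalamin failure rate. I vary the latter from 10 to 50% for the comparison between arms, and from 20 to 64% for the count of patients left.
- SVR at 30 minutes is normal, and failure means SVR below 500.

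**Step 1. Patients left in the comparison**

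Failure rate f = 9/14 = 0.643, exact (Clopper-Pearson) 95% CI 0.351 to 0.872. Expected number retained = 10 × (1 − f):
- f = 0.643: 3.6
- f = 0.351: 6.5
- f = 0.872: 1.3

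At f = 9/14 the binomial probability that 3 or fewer of 10 remain is 49%. With hydroxocobalamin failure of 20 to 64%, the total left is 3.6 + 8.0 = 11.6 down to 3.6 + 3.6, about 7, of 20.

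Only if 3.1 exclusions were replaced, which no section states: methylene blue patients to be treated to retain 10 = 10/(1 − f) = 28 at 0.643 and 15 at 0.351, against 20 planned in both arms together.

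**Step 2. Effect within one arm**

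Let z = Φ⁻¹(f) and λ = φ(z)/(1 − f). Retaining only SVR of at least 500 raises the mean by λ SDs and multiplies the SD by √(1 + zλ − λ²).

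| f | Rise in mean (SD) | SD ratio |
|---|---|---|
| 0.10 | 0.19 | 0.84 |
| 0.30 | 0.50 | 0.70 |
| 0.50 | 0.80 | 0.60 |
| 0.643 | 1.04 | 0.54 |

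**Step 3. Effect on the difference, equal SDs**

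With M for methylene blue and H for hydroxocobalamin, the all-treated difference is (z_M − z_H) SDs. The share lost by retaining only responders is (λ_M − λ_H)/(z_M − z_H).
- f_M = 0.643, f_H = 0.10: (1.045 − 0.195)/(0.366 + 1.282) = 0.52
- f_M = 0.643, f_H = 0.50: (1.045 − 0.798)/(0.366 − 0) = 0.67
- f_M = 0.872, f_H = 0.10 to 0.50: 0.60 to 0.74
- f_M = 0.351, f_H = 0.10: 0.42

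For example, with SD 200 and f_H = 0.30, an all-treated difference of 178 becomes 69. A simulation with 2 million patients per arm gave the same two figures.

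**Step 4. Unequal SDs** (f_M = 0.643, f_H = 0.36)

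All-treated mean = 500 − z × SD; retained mean = that + λ × SD.
- SD 100 on methylene blue, 200 on hydroxocobalamin: all-treated 463 and 572, difference 108; retained 568 and 689, difference 121.
- SDs swapped: all-treated 427 and 536, difference 109; retained 636 and 594, difference −41.

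**The case against.** The best case for leaving the plan alone is that this is a descriptive pilot with no planned test, so type I error is not at stake. Section 7.3 is the section on analysis populations and already has the right rule, while 3.1 is a general description that leaves room to report failure rates. This limits the kind of harm but does not remove it. Section 3.1 states its exclusion without qualification, nothing ranks 7.3 above it, the objective is comparative, and 7.1 wants the data for planning.

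Several narrower points stand:
- The figures apply to the 30-minute SVR level only. For a measure less closely tied to it the effect is smaller: at 64% failure and an assumed correlation of 0.5, the mean rises by 0.5 × 1.045 = 0.52 SD and the SD ratio is √(1 − 0.25 × (1 − 0.54²)) = 0.91.
- That each arm looks better than its all-treated result holds for values taken before the second drug. Later values include that drug's effect, and the sign is then not assured.
- The 9/14 rate is a small series under another definition. The sign reversal needs a two-fold SD ratio for which the document gives no evidence.
- Section 4.4.1 reads partly as template text, since it refers to missed visits in an intraoperative study. Section 9.1 partly answers the data question: after a subject revokes authorization, the investigator "retains the ability to use all information collected prior to the revocation of subject authorization". It covers revocation, not treatment failure.
- Only the reconciliation of sections follows strictly from the contradiction. Using values before the second drug is one reasonable choice of estimand among several.

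**Conclusion.** The concern holds and must be fixed. Sections 3.1 and 7.3 give incompatible populations for the primary comparison, and the 3.1 rule conditions on a component of the primary endpoint. Both conclusions come from the text and depend on none of the assumed numbers.

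The size is illustrative. It rests on normal 30-minute SVR, failure defined as SVR below 500, the 9/14 rate and assumed hydroxocobalamin rates. On those terms the methylene blue arm falls to about 3.6 of 10 (1.3 to 6.5 over the confidence interval), and the drug difference shrinks by roughly half to two-thirds when SDs are equal. When SDs differ, neither the size nor the direction of the responder-only difference can be relied on.

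**What to change.** 1. **Section 3.1:** replace the exclusion sentence with a statement that all treated patients are analysed in their assigned arm, including those who receive the second drug. Section 7.3 then governs.
2. **Sections 3.4 and 7.3:** state that the hemodynamic comparison uses values recorded before any second drug, and name the time point. Thirty minutes is one option, because 3.1 already assesses persistence then.
3. **Failure outcome:** require the number and percentage, by arm, with persistent vasoplegia at 30 minutes or receipt of the second drug. Section 7.2 already provides for this kind of summary.
4. **Section 4.4.1:** reconcile it with 7.3. Data already collected are kept, treatment failure or an adverse event does not end collection from the medical record, and treated patients are not replaced in the analysis.

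The rescue rule itself is untouched. The cost is wording and a little more analysis, with no added patients or procedures. The values should already be on record, since 3.4 notes: "The monitoring and documentation of hemodynamic values is part of SOC practice during LT surgery".

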3.2 Number of Subjects

Twenty

3.3 Duration of Participation

Intraoperatively during LT surgery

3.4 Primary Study Endpoints

The primary endpoint of the study will be the improvement in hemodynamic values as measured by SVR, systemic blood pressure, and amount of vasopressors administered. The monitoring and documentation of hemodynamic values is part of SOC practice during LT surgery.

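### The primary endpoint has no pre-dose reference, reading time, window or vasopressor scale, and the plan conflicts on patients who receive the second drug

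*Combined protocol and SAP*

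**What the plan says.** Section 3.4 defines the primary endpoint as "improvement in hemodynamic values as measured by SVR, systemic blood pressure, and amount of vasopressors administered". The primary objective in Section 2 uses nearly the same words, "improving hemodynamic stability as measured by SVR, systemic blood pressure, and amount of vasopressors administered". Section 3.1 says of data capture only that "The SVR, blood pressure, and amount of administrations will be recorded". Section 3.3 gives the duration of participation as "Intraoperatively during LT surgery". Section 7.2 lists summary statistics and adds no window, rate or adjustment for duration.

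Two timed rules exist, and neither belongs to the endpoint. Section 8.1 sets a 90-minute adverse event period. Section 3.1 brings in the other active drug: "If the patients still present with vasoplegic syndrome 30 minutes after receiving IV methylene blue or hydroxocobalamin during LT surgery", the treatment not yet received is used.

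Three sections bear on the analysis of those patients:
- Section 3.1: "The patients will be excluded from the comparison study, but the data of frequency of failure to effectively treat vasoplegia" may be used to describe how often treatment fails.
- Section 7.3: "Each participant who received the study drug will be included in the primary analysis regardless of study withdrawal for any reason".
- Section 4.4.1: a need for another form of treatment is a reason for withdrawal, and data are not collected on withdrawn subjects.

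**The concern.** An amount of drug means little until one knows over what period it was given, from what starting point and in what unit. If it is added up over the rest of the operation, it grows with the time left in surgery as well as with the patient's need for vasopressors. Amounts of different vasopressors cannot be added without a conversion. SVR and blood pressure share part of the problem, because no reading time is set for them either.

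The 30-minute rule makes the missing time point matter more. A value read after it may come from a patient who has had both drugs. Whether that patient is in the comparison depends on which section the analyst follows.

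At stake is what the pilot hands on. Section 7.1 says its purpose is feasibility and descriptive data from which later power can be obtained. Two analysts could choose different windows and analysis sets, both consistent with the text, and pass different standard deviations and different arm contrasts to the next trial.

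**Working it through.** There is no power calculation to reproduce. Section 7.1 says the information was insufficient for one, and 20 patients is a pilot choice. The checks below size the consequences of the open definition.

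**Inputs from the documents.** 10 patients per arm (Section 3.1); other drug from 30 minutes (Section 3.1); 9 of 14 methylene blue patients with an ineffective response (Section 1.3).

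**Assumptions.** The documents give no operating times, infusion rates or variances. The times, the coefficients of variation (CV) and the effect of the second drug used below are all assumed.

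**1. Chance difference from operating time, if the amount is a total to the end of surgery.** Let the infusion rate be identical in every patient, so that the total varies only with remaining time. The 95% range for the relative difference between arm means is ±1.96 × CV × √(2/10).
- CV 20%: 1.96 × 0.2 × 0.447 = 0.18
- CV 40%: 1.96 × 0.4 × 0.447 = 0.35
- CV 60%: 1.96 × 0.6 × 0.447 = 0.53

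As an example, a rate that is truly 30% lower gives a total 5% higher if 90 minutes remain in that arm against 60 in the other: 0.7 × 90/60 = 1.05.

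**2. Effect on the variability passed to the next trial.** If rate and remaining time are independent, CV of the total = √[(1 + CV_rate²)(1 + CV_time²) − 1].
- Both 0.5: √(1.25 × 1.25 − 1) = 0.75
- Rate 0.5, time 0.3: √(1.25 × 1.09 − 1) = 0.60

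For the same relative effect, sample size scales with CV². The factors are (0.75/0.5)² = 2.25 and 0.3625/0.25 = 1.45.

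**3. How many patients the second-drug conflict could touch.** Section 1.3 reports "Nine out of 14 patients receiving MB had an ineffective response": 9/14 = 64%, exact (Clopper-Pearson) 95% CI 35% to 87%. If that rate carried over:
- About 6.4 of 10 methylene blue patients would meet the second drug (3.5 to 8.7 over the interval).
- About 3.6 of 10 would not (1.3 to 6.5).

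**4. Consequence under each reading.**
- *Section 7.3 governs (patients kept).* Values after 30 minutes mix both drugs. If 60 or 120 minutes remain, (60 − 30)/60 = 50% or (120 − 30)/120 = 75% of a window to the end of surgery lies after that point. If the second drug halved the later infusion rate, the methylene blue arm's mean total would fall by 0.643 × 0.5 × 0.50 = 16% or 0.643 × 0.5 × 0.75 = 24%.
- *Section 3.1 governs (patients excluded).* There is no mixing. Failures of the assigned drug are removed, and each arm keeps only patients selected because that drug worked.
- *Section 4.4.1 applied as well.* If these patients count as withdrawn, their data may not be collected, and Section 7.3 could not then be carried out.

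**5. Same check with a fixed early window.** If each component is read no later than 30 minutes and before any second drug, the second drug contributes none of the window. For an infusion rate, remaining operating time drops out.

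**The case against.** The best defense is that the text never calls the amount a total, cumulative or taken to the end of surgery. The word improvement implies a comparison with an earlier state, and the chart review in Section 1.3 describes its vasopressor result as an average change in requirements. A before-and-after reading is at least as natural. This stands. A reader might infer that the endpoint does measure operating time; the documents support only that it could, because nothing rules that reading out.

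A reader might also infer that the second drug contaminates the comparison and draws the arms together. That does not follow either. Section 3.1 excludes those patients, so mixing arises only if Section 7.3 prevails. Even then the direction is unknown, because no failure rate is given for hydroxocobalamin used first.

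The ±35% is symmetric chance variation under randomization, on an assumed CV. It is not bias. The 9/14 is retrospective, covers methylene blue only, and defines failure as no improvement in hemodynamics or no reduction in pressor requirement, which is not the 30-minute rule.

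Finally, the trial is a descriptive pilot with no planned test, so no formal conclusion can be overturned. That lowers the severity. It does not remove the point, because supplying figures for a later power calculation is the pilot's stated use.

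**Conclusion.** The concern holds in a limited form. The primary endpoint lacks a pre-dose reference, reading time, window, rate and common vasopressor scale throughout the documents, and Sections 3.1, 4.4.1 and 7.3 conflict on patients given the second drug. Both ways of resolving that conflict cause trouble if the endpoint is read late: one mixes two drugs, the other selects responders.

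If the amount is taken as a total to the end of surgery, chance differences in remaining time alone would move arm means by about ±18% to ±53% over assumed time CVs of 20% to 60%. The sample size planned from it for the next trial could be inflated by 1.45 to 2.25 times under the assumed CVs. If a before-and-after rate is what the sponsor intends, these figures do not apply and the remaining fault is that the plan does not say so. The number of patients affected by the conflict cannot be pinned down; about 6 of 10 in the methylene blue arm is an illustration from 9/14.

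This is a cheap improvement of modest severity. The sample size of 20 is not in question.

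**What to change.** In Section 3.4, define SVR, blood pressure and vasopressor use each as the change from the last pre-dose value to one fixed time, no later than 30 minutes after the assigned drug and before any second drug. State whether the clock runs from the start or the end of the infusion; counting from the start keeps the reading at or before the 30-minute point on either interpretation. Express vasopressor use as a dose rate on one prespecified equivalence scale, over pre-dose and post-dose windows of equal length.

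Reconcile Sections 3.1, 4.4.1 and 7.3 so that every treated patient contributes this value, taken before any second drug, and report second-drug use by arm as an outcome of its own. Failures then need not be dropped, because their value precedes the second drug. The change concerns measurement and analysis only and leaves the timing of treatment as it is.

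The cost is one paragraph in Section 3.4, aligned wording in the three sections, and a conversion table fixed before the first patient. There are two drawbacks. Equivalence factors are approximate. The availability of time-stamped vasopressor rates is also assumed: Section 3.7 lists vital signs and intraoperative events in the electronic record but does not mention such rates, so this should be confirmed first.
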